PROTOCOL TITLE:

Naloxone Auto-injector as a Universal Precaution for Patients with Opioid Substance Use Disorder (DSM-V)

PRINCIPAL INVESTIGATOR:

Name: [name]. Department: Neurosurgery

VERSION NUMBER:

Version 5.0

DATE:

9/11/2018

REGULATORY FRAMEWORK:

Please indicate all that apply:

DOD (Department of Defense)
DOE (Department of Energy)
DOJ (Department of Justice)
ED (Department of Education)
EPA (Environmental Protection Agency)
FDA (Food and Drug Administration)
HHS (Department of Health and Human Services)
Other:

If yes, please confirm that the research team is familiar with and agrees to comply with the investigator requirements cited in ICH-GCP E6. Yes No ICH-GCP E6 can be accessed by copying and pasting this URL into your browser: http://www.fda.gov/downloads/Drugs/Guidances/ucm073122.pdf

Table of Contents

1.	Objectives	3
2.	Background	3
3.	Study Design	8
4.	Inclusion and Exclusion Criteria	8
5.	Number of Subjects	8
6.	Study Timelines	9
7.	Study Endpoints	9
8.	Research Setting	9
9.	Resources Available	
10.	Prior Approvals	
11.	Multi-Site Research	14
12.	Study Procedures	14
13.	Data Analysis	15
14.	Provisions to Monitor the Data to Ensure the Safety of Subjects	16
15.	Withdrawal of Subjects	16
16.	Data Management/Confidentiality	17
17.	Data and Specimen Banking	19
18.	Risks to Subjects	19
19.	Potential Benefits to Subjects	
20.	Recruitment Methods	
21.	Provisions to Protect the Privacy Interests of Subjects	
22.	Economic Burden to Subjects	
23.	Compensation	
24.	Compensation for Research-Related Injury	
25.	Consent Process	
26.	Documentation of Consent	
27.	Study Test Results/Incidental Findings	
28.	Sharing Study Progress or Results with Subjects	
29.	Inclusion of Vulnerable Populations	
30.	Community-Based Participatory Research	
31.	Research Involving American Indian/Native Populations	
32.	Transnational Research	
33.	Drugs or Devices	
Che	cklist Section	

1. Objectives

To conduct a pilot study of a naloxone auto-injector in a "Universal Precaution" manner for patients with opioid substance use disorder. Our three objectives are:

- 1) To decrease the number of fatal and nonfatal overdose deaths by use of the naloxone auto-injector by co-prescribing in the University of New Mexico Addiction and Substance Abuse Program (UNM ASAP).
- 2) To study the characteristics of the study subjects who performed the overdose reversals (vs. the study subjects who did not) using a biostatistical logistic regression analysis

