Since April 2016, we have enrolled 358 patients at ASAP in our prospective nonrandomized clinical trial using the Evzio autoinjector. We have documented 82 overdose reversals thus far. Only one of the reported overdose reversals was from the study patients at ASAP, while the other 81 overdose reversals were from community members received naloxone from the study patients. For every 100 patients enrolled in the study, approximately 23 overdose reversals have been reported. We have submitted a peer-reviewed article about this data, and are now waiting to hear back regarding acceptance of the submission.

3. Study Design

- 3.1. The previous study at ASAP is a prospective observational study using the naloxone 0.4 mg auto-injector which took place April 4th, 2016 through April 30th, 2017.
- 3.2. Evaluation of patients enrolled include: # overdoses reversed, # naloxone doses needed, urine toxicology, history of overdoses witnessed, history of being reversed by naloxone, demographic information, medical history, etc.
- 3.3. For this current study, we propose the following new additional studies:
 - A biostatistical logistic regression analysis to study the characteristics of the study subjects who performed the overdose reversals (vs. the study subjects who did not).

8 | [Type text]

- A qualitative study to examine in-depth the characteristics of study subjects who a) documented many overdosed reversals/"saved" many community members, b) documented one overdose reversal/"saved" one community member, and c) did not document any overdose reversals
- Study the 2 mg Evzio autoinjector product to prospectively analyze the difference in doses (2 mg vs. 0.4 mg) needed to reverse an overdose. The goal will be to recruit 100 patients in one year and document between 20-30 overdose reversals in the community.

4. Inclusion and Exclusion Criteria

Inclusion Criteria

- A. All patients treated with naltrexone, methadone or buprenorphine as medication assisted treatment at the UNM Addiction and Substance Abuse Program (UNM ASAP) aged 18 or older.
 - Over 70% of patients at UNM ASAP on medication assisted treatment use methadone
- B. Subjects who sign a consent form.

Exclusion Criteria

- A. Subjects who are allergic to naloxone and its inactive ingredients.
 - Inactive ingredients: buffering agents
- B. Subject younger than 18.

5. Number of Subjects

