The University of New Mexico Addiction and Substance Abuse Program (UNM ASAP) will be the research site, to include all subjects with a DSM-V diagnosis of substance use disorder. The UNM ASAP treats approximately 600 patients for substance use disorders with diagnosis of opioid dependence disorder annually. Ninety percent of these patients are treated daily as a part of their federally funded methadone maintenance treatment program. The remainder are treated with buprenorphine or naltrexone as opioid replacement therapy. Naltrexone has an FDA indication to treat opioid dependence.

We will explain the study to all potential candidates; however, 20-30% of the patients may decline to participate in the study.

We are enrolling study subjects at a current rate of approximately 6-10 subjects per month and anticipate this continuing throughout the year. Additionally, we can anticipate that our current study population is reporting a steady overdose reversal rate of 23% for every 100 patients enrolled. This number has not changed since July 2016.

Power analysis: the occurrence of opioid overdose death at the UNM ASAP is approximately 10% annually. With a sample size of 500 people we will have 80% power to detect a 20% difference in mortality at alpha level of 0.05.

6. Study Timelines

The research team submitted the initial IRB application at the beginning of October 2015. Recruitment at UNM ASAP will start in January 2016, after receiving IRB approval. The research team will follow the study subjects for one year and will close the study when qualitative interviews have been completed.

If the IIS is approved, the research team will begin the logistic regression analysis as soon as possible. Once the IRB approves the qualitative modifications, the face-to-face 1:1 interviews will begin with the study subjects.

The recruitment for the Second Year Study will begin June 1, 2017 at UNM ASAP, after receiving IRB approval for protocol amendment. The research team will follow a study subject for one year and will close the study when qualitative interviews have been completed.

7. Study Endpoints

There are four endpoints in this study:

- 1. Number of fatal over dose deaths and near fatal overdoses averted by use of naloxone auto-injector co-prescribing from the University of New Mexico Addiction and Substance Abuse Program (UNM ASAP)

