Investigators at UNM ASAP will distribute naloxone rescue kits to all study subjects. Naloxone is a prescription medication administered intravenously, subcutaneously or intramuscularly. In this study, the research team will use the naloxone auto-injector which is the only product FDA approved and labeled for use by family members or caregivers for emergency therapy wherever opioids are present. The research team will distribute the kits at the initial visit and provide education on drug overdose and rescue method from an overdose (education materials: see Appendix 2: A Patient's Guide to Evzio and Appendix 9: Opioid Overdose Toolkit) upon receiving informed consent. The education material covers education on opioid overdose and how to use the auto-injector. Education will be provided not only for patients but also, if the patient agrees, their bystander (bystander is defined as a caregiver, such as family member, friend, etc.) at initial visit and follow-up visits. According to the New Mexico Good Samaritan Law, any bystanders of patient are able to provide naloxone when drug overdose occurs. Thus, we will educate patients and their bystanders on the signs and symptoms of drug overdose due to opioids, drug overdose deaths and its risks (Appendix 9), how to use naloxone auto-injector (Appendix 2). If the patient would like to be enrolled in the study without a bystander present, he/she will be educated on the use of intramuscular naloxone and asked that they educate their friends and/or family. The subjects will return to UNM ASAP every three months after the initial visit for a follow-up. The following figure describes the procedures the investigator will carry out during each visit.

Initial Visit: Assess inclusion/exclusion criteria, obtain consent, results of urine drug screening test, and baseline information, provide face to face opioid education (individual or group education – up to 6 people in a group) and how to use naloxone auto-injector, and distribute one naloxone auto-injector carton prior to the next study visit (there are 2

14 | [Type text]

naloxone auto-injector per carton).

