Follow-up Visit (every three months): Obtain results of urine drug screening test, monitor frequency of naloxone auto-injector use, reason for naloxone auto-injector use, provide face to face education, as needed and refill naloxone auto-injector kit as needed. When patients report opioid overdose at these follow-up visits, we will obtain further information on the overdose via patient interview. The information will include date, time, and dose of naloxone use, clinical outcome [i.e., successful opioid reversal, death, and utilization of healthcare institution (e.g., EMS, emergency room, hospitalization)], to whom the kits were used, causality [i.e., type(s) of opioid], and call 911 after utilization of the kit. We will confirm the record by accessing PowerChart, only if patients used UNM Hospital for treatment.

Month 12 (1 Year): End of study visit: Obtain results of urine drug screening test, continue to ask same questions as in Follow-up visit.

If a patient uses the naloxone prior to the scheduled clinic visit, the study team will distribute one naloxone auto-injector carton prior to the next study visit. The study team will inquire about the circumstances for the use of the naloxone auto-injector.

Optional qualitative sub-study: If a study subject is selected as a potential candidate for the qualitative study, they may be contacted by phone or in person during one of their clinic visits and have the optional sub-study consent explained to them. If the person agrees to be interviewed, this will be done at a private consult room at ASAP. This visit may take 30-45 min at the end of which they will receive a \$20 gift card.

13.Data Analysis

Statistical Analysis

Statistical analysis will be performed using STATA (College Station Texas) and SAS version 9.3 (Cary, NC, United States).

The research team will collect the data and will use a descriptive analysis for demographic, social status, medical history, physical examinations, including vital signs (normal vs. abnormal findings), number of concomitant medications, scores of RIOSORD, and outcome related parameters listed in Section 12.

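### The stated 80% power for a 20% difference in mortality with 500 people does not reproduce; a 20% relative change gives about 11% to 38% two-sided

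*Combined protocol and SAP*

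**What the plan says.** The power analysis in Section 5 (Number of Subjects) is two sentences. The first gives the base rate: "the occurrence of opioid overdose death at the UNM ASAP is approximately 10% annually". The second gives the claim: "With a sample size of 500 people we will have 80% power to detect a 20% difference in mortality at alpha level of 0.05". The same section expects that "20-30% of the patients may decline to participate in the study".

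Overdose death is a headline outcome. Objective 1 in Section 1 begins "To decrease the number of fatal and nonfatal overdose deaths by use of the naloxone auto-injector", and endpoint 1 in Section 7 is the "Number of fatal over dose deaths and near fatal overdoses averted by use of naloxone auto-injector co-prescribing".

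On design, Section 2 (Year 1- ASAP Study) describes a "prospective nonrandomized clinical trial using the Evzio autoinjector", and Section 12 states that "Investigators at UNM ASAP will distribute naloxone rescue kits to all study subjects". Subjects are followed for one year (Section 6). At follow-up visits a reported overdose is recorded with its "clinical outcome [i.e., successful opioid reversal, death, and utilization of healthcare institution" among other items. Section 13 summarises outcome parameters descriptively. The variables it lists for chi-square, Fisher, t or rank-sum tests do not include mortality.

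**The concern.** A power figure can be checked only if the effect, the comparator, the test and the sidedness are known. Section 5 gives the sample size, base rate, alpha and power, and leaves those four open. The usual reading of a 20% difference from a 10% base is a relative change of one fifth, to 8%. That is two percentage points on a fairly rare event, and 500 people looks far too few for it. The absolute reading fails outright, because mortality cannot fall 20 points from 10%.

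This is the only power statement in the text I read, and it concerns the outcome in objective 1 and endpoint 1. It tells the IRB and later readers that a one-fifth change in mortality would be detected four times in five. If that is wrong by a wide margin, a finding of no mortality difference could be taken as good evidence of no effect.

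**Working it through.** **Inputs.** All from Section 5: N = 500, base rate 10% per year, alpha 0.05, stated power 80%. Follow-up is one year (Section 6), so the annual rate needs no rescaling. Sidedness is not stated; two-sided is taken first. The critical values are 1.960 for alpha and 0.842 for 80% power.

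**Attempt to reproduce 80%: relative reading, 10% against 8% or 12%.**

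*One cohort of 500 against a fixed 10%.* Power = Φ[(0.02 − 1.960·SE₀)/SE₁], with SE₀ = √(0.10·0.90/500) = 0.01342.
- 8%: SE₁ = √(0.08·0.92/500) = 0.01213; (0.02 − 0.02630)/0.01213 = −0.519; power 30%.
- 12%: SE₁ = √(0.12·0.88/500) = 0.01453; (0.02 − 0.02630)/0.01453 = −0.433; power 33%.
- Exact binomial: 29% (reject at 36 or fewer deaths) and 26% (reject at 65 or more).
- Arcsine: 35% and 30%.
- Wald with the alternative standard error: 38% and 28%.

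*Two equal groups, pooled z test.* Power = Φ[(0.02 − 1.960·SE₀)/SE₁], with SE₀ = √(2·p̄(1 − p̄)/n) and SE₁ = √([p₁(1 − p₁) + p₂(1 − p₂)]/n).
- 250 per group, 8%: SE₀ = 0.02560, SE₁ = 0.02558; argument −1.179; power 12%.
- 250 per group, 12%: SE₀ = 0.02799, SE₁ = 0.02797; argument −1.246; power 11%.
- 500 per group: 20% (8%) and 17% (12%).

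| Design | Two-sided, 8% / 12% | One-sided, 8% / 12% |
|---|---|---|
| 500 against fixed 10%, z test | 30% / 33% | 43% / 44% |
| Same, exact binomial | 29% / 26% | 41% / 41% |
| Same, Wald | 38% / 28% | 50% / 39% |
| 250 per group | 12% / 11% | 19% / 18% |
| 500 per group | 20% / 17% | 29% / 26% |

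Unpooled and arcsine two-group versions differ from the pooled figures by less than half a percentage point. A time-to-event view agrees: a hazard ratio of 0.8 needs 4·(1.960 + 0.842)²/(ln 0.8)² ≈ 631 deaths at 1:1. Two groups of 250 at 10% and 8% would give 25 + 20 = 45.

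**Absolute reading.** 10% − 20 points is impossible. For 10% against 30% at 250 per group, power exceeds 99.9%.

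**Size needed for 80% two-sided power, 10% against 8%.**
- Fixed 10%: [(1.960·0.3 + 0.842·√0.0736)/0.02]² ≈ 1,666 people.
- Two groups: [1.960·√(2·0.09·0.91) + 0.842·√(0.09 + 0.0736)]²/0.02² ≈ 3,213 per group.

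**Fall detectable at 80% two-sided power.**
- 500 against fixed 10%: to about 6.4% (36% relative).
- 250 per group: to about 3.7% (63% relative).
- 500 per group: to about 5.3% (47% relative).

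**Search for a route to both 500 and 80%.** Reading the 20% as the second group's rate, 10% against 20% needs [1.960·√(2·0.15·0.85) + 0.842·√(0.09 + 0.16)]²/0.10² = 198.96, so 199 per group or 398 people. Then 398/0.80 = 497.5, close to 500, if the lower refusal figure of 20% is treated as dropout. Power for this comparison is 80% at 200 per group, 75% at 175 per group (30% refusal) and 88% at 250 per group. An unequal split of 383/117 (10% in the larger group) gives 79% with no inflation. Both routes are guesses: the protocol states neither.

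**The case against.** The strongest reply is that the sentence carries little weight. The work is called a pilot, Version 5.0 postdates most of the enrolment, and the added components (logistic regression, interviews, the 2 mg phase) do not use the mortality power. No test or stopping rule in the text I read depends on the 80%. This is true, and it limits the harm to the claim itself. It does not make the claim right: a pilot need not be powered for mortality, but then it should not say that it is.

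A second reply is that the author may have meant 10% against 20%, so the fault is an undefined effect and not a miscalculation. That is possible. But a doubling is not a 20% difference, it runs against an objective of decreasing deaths, it needs a second group when every subject gets a kit, and refusal before consent is not dropout. Even if it was intended, the sentence misdescribes it.

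A third reply is that 11% to 38% is not a range over all designs. This is fair. The upper end comes only from the one-sample Wald form, and the lower end assumes equal groups; a 400/100 split gives about 7% to 11%. Unequal splits lower power further, so the conclusion stands.

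Two smaller points also stand. The 2 mg phase has its own target of 100 patients and 20-30 reversals, but that is a recruitment goal without a power calculation. Part of the protocol between Sections 9 and 12 was not in the text I read, so a comparator might be named there. That would not restore 80% for a 20% relative change in any design tried with 500 people.

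**Conclusion.** The concern holds. As written, 500 people do not give 80% power for a 20% difference in mortality from a 10% base at alpha 0.05. On the relative reading, power is about 11% to 38% two-sided for equal groups or a fixed comparator, and at most about 50% one-sided. On the absolute reading, the fall is impossible and the rise gives nearly 100%. The shortfall is large: 80% power for 10% against 8% needs about 1,666 people against a fixed rate, or 3,213 per group.

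These figures take the protocol's 10% at face value, though no source is given for it, and assume one year of complete follow-up. The choice of design moves the number but never brings it near 80%. The statement must be corrected. Study conduct is not affected.

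**What to change.** Delete the mortality power sentence in Section 5 and report deaths descriptively, in line with Section 13's treatment of outcome parameters. The death item in Section 12 is the outcome of a reported overdose, and 81 of the 82 Year 1 reversals were in community members. The text should therefore say whether the deaths reported are those of study subjects or of people given a kit.

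Alternatively, keep a power statement but name the comparator and test, give the source of the 10%, say whether the difference is relative or absolute, and restate the figure:
- Against a fixed 10%: about 30% two-sided power for 10% against 8%, or 80% only for a fall to about 6.4% (36% relative).
- With 250 per group: about 12% power, or 80% only for a fall to about 3.7% (63% relative).
- If 10% against 20% was intended: call it a doubling, name the second group, and show how 500 was reached.

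The cost is wording only, with no extra patients, visits or data. The plan loses a claimed 80% or replaces it with a less favourable figure.

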- 2. To study the characteristics of the study subjects who performed the overdose reversals (vs. the study subjects who did not) using a logistic regression analysis
- 3. To qualitatively study the in-depth characteristics of study subjects who a) documented many overdosed reversals/"saved" many community members, b) documented one overdose reversal/"saved" one community member, and c) did not document any overdose reversals
- 4. Study the 2 mg Evzio autoinjector product to prospectively analyze the difference in doses (2 mg vs. 0.4 mg) needed to reverse an overdose. The goal will be to recruit 100 patients in one year and document between 20-30 overdose reversals in the community. (Between April 4th 2016 and April 4th 2017, 383 study subjects were enrolled and there were 93 reported overdose reversals)We are currently enrolling new patients at the rate of 6-10 new patients per month.

8. Research Setting

Research facility: The study is conducted at UNM ASAP.

UNM's ASAP is a part of the behavioral health program under the UNM Psychiatric Center. ASAP specializes in providing diverse, proven substance abuse and mental health treatment, including specialized services for women. ASAP provides services to adults and adolescents with a primary substance abuse diagnosis and/or individuals who have a substance abuse disorder along with other mental health issues. Location: [name]

9. Resources Available

Study personnel Principal investigator:

[name] MD, professor, Department of Neurosurgery, School of Medicine As medical director and founder of the UNM Pain Center and ECHO Pain clinic at the

10 | [Type text]

University of New Mexico, [name] has played key roles in improving access to specialty care for chronic pain patients, as well as in improving the quality of care by providing consultative, educational, and therapeutic services to patients throughout New Mexico. She has a broad background in neurology, pain and headache management, neurorehabilitation, and traumatic brain injury, and for the past three years she has effectively led the interdisciplinary team of pain specialist at Project ECHO. She will serve as an investigator on this project. This proposed project is a collaboration study with the New Mexico Department of Health and will definitely reduce drug overdose deaths, which are a serious public health issue in New Mexico.

Co-investigators (alphabetical order)

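### Section 5 ties its power claim to 500 people, but enrolled plus goal gives 483, and the stated accrual rate reaches 500 only towards its upper end

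*Combined protocol and SAP*

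**What the plan says.** Section 5 (Number of Subjects) contains the only power statement: "With a sample size of 500 people we will have 80% power". It claims "80% power to detect a 20% difference in mortality at alpha level of 0.05", and the sentence before it gives the baseline: "the occurrence of opioid overdose death at the UNM ASAP is approximately 10% annually".

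The same section describes the source of subjects. "The UNM ASAP treats approximately 600 patients" with opioid dependence a year, and "20-30% of the patients may decline to participate in the study". On pace, it says the team is "enrolling study subjects at a current rate of approximately 6-10 subjects per month" and expects this to continue through the year.

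Endpoint 4 in Section 7, repeated in Section 1, gives two further counts. Between April 4, 2016 and April 4, 2017, "383 study subjects were enrolled". For the 2 mg product, "The goal will be to recruit 100 patients in one year".

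Section 3.1 calls the 0.4 mg phase the previous study and dates it to April 30, 2017. Section 6 starts Year 2 recruitment on June 1, 2017.

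**The concern.** A sample size that supports a power claim should be traceable to a cohort the study will have. Here, 500 is neither the completed 0.4 mg phase nor the 2 mg phase. It can only be approached by adding the two, and the plan does not say that it adds them. Section 3.3 and endpoint 4 set the two products against each other on doses needed.

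Even if they are added, enrolled plus goal stops short of 500. A reader or ethics board relying on Section 5 would credit the mortality question with a size that the other sections do not deliver, and could not tell which subjects the claim covers.

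**Working it through.** **Inputs**
- Power statement: 500 people, 80% power, 20% difference, alpha 0.05, baseline 10% a year (Section 5). Number of groups, sidedness, and whether 20% is relative or absolute are not stated.
- Pool: about 600 a year, 20-30% may decline (Section 5).
- Enrolled: 383 at April 4, 2017; Year 2 goal: 100 in one year (Sections 1 and 7).
- Rate: 6-10 a month (Sections 1, 5 and 7).

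**Step 1. Can the plan's own figure be reproduced?** Take 20% as relative, so 10% against 8%. For two equal groups of n, with the normal approximation and pooled variance under the null:

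power = Φ{[0.02 − 1.96·√(2·0.09·0.91/n)] / √[(0.10·0.90 + 0.08·0.92)/n]}

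With n = 250 this is 11.9% two-sided (19.4% one-sided). For a single group of 500 against a fixed 10%:

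power = Φ{[0.02 − 1.96·√(0.09/500)] / √(0.0736/500)} = 30.2% two-sided (43.2% one-sided)

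An absolute fall of 20 points from 10% is impossible. An absolute rise to 30% gives more than 99.9% with 250 per group. None of these readings gives 80% at 500 people, so the power calculation does not explain where 500 came from.

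**Step 2. Does the recruitment information give 500?**

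| Route | Arithmetic | Result |
|---|---|---|
| One year's pool | 600 × 0.70 to 600 × 0.80 | 420-480 |
| Enrolled plus goal | 383 + 100 | 483 |
| Stated rate, 12 months from April 4, 2017 | 383 + 12×6 to 383 + 12×10 | 455-503 |
| Stated rate, about 14 months (to June 1, 2018) | 383 + 14×6 to 383 + 14×10 | 467-523 |

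**Step 3. How far up the stated range is 500?** Subjects still needed: 500 − 383 = 117.
- Over 12 months: 117/12 = 9.75 a month, close to the top of 6-10.
- Over 14 months: 117/14 = 8.36 a month, above the midpoint. At 8 a month the total is 383 + 112 = 495.
- Time needed at 10 and at 6 a month: 117/10 = 11.7 months and 117/6 = 19.5 months.

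**Step 4. What would the pool have to be?** 500/0.80 = 625 and 500/0.70 ≈ 714, which is 25 to about 114 more patients than one year's 600.

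**Step 5. How much does the gap matter?** 500 − 483 = 17, and 17/500 = 3.4%. The Step 1 formulas, two-sided, give:
- two equal groups: 11.6% at 483 in total, against 11.9% at 500;
- single group: 29.2% at 483, against 30.2% at 500.

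**The case against.** The strongest reply is that 500 is attainable, and this stands. Four parts of it are sound.

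- The 600 is an annual count, while recruitment runs over more than one year. The documents give no turnover figure, so 420-480 cannot be used as a cap. The 20-30% is also only what may decline.
- 383 is a count at April 4, 2017, and the 0.4 mg phase ran to April 30. If 6-10 a month continued to April 30 (about one month) and the goal of 100 was then met, the total is 489-493. If it continued to June 1 (about two months), the total is 495-503.
- 100 is a goal and not a maximum, and no recruitment end date is given. The 12-month range at the stated rate already includes 500.
- A gap of 17 is statistically trivial.

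A reader might therefore infer from 420-480 and 483 that 500 is out of reach. The documents do not support that.

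A reader might also set the 100-patient goal against 500 and conclude that the 2 mg phase is grossly undersized. That comparison is not fair. The 500 is attached to mortality, which belongs with endpoint 1, while the goal of 100 belongs to the dose question in endpoint 4. Nothing says that the 2 mg cohort was meant to supply 500.

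The reply does not supply a derivation of 500, a statement of which subjects it counts, or a reason to plan on the upper part of the accrual range. The 6-10 a month is the plan's own forecast, so it already reflects whatever turnover the clinic has.

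**Conclusion.** The point holds in a limited form. Section 5 attaches its power claim to a size that the plan does not derive and does not assign to any cohort. Enrolled plus goal gives 483, which is 17 (3.4%) short. The stated rate reaches 500 only near its top over 12 months, and only in its upper half over about 14.

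The shortfall alone is worth about one percentage point of power or less. The weight of the point lies in the unassigned number and in the claim resting on it. That claim also fails to reproduce at 500, which is a separate and larger fault in the same sentence.

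Assumptions: a constant 6-10 a month from April 4, 2017; no subject counted in both phases; two equal groups, or one group against a fixed 10%, for the power figures. The text from part of Section 9 to the start of Section 12 was not available for this review. A statement there on pooling or on total enrolment would answer the assignment question, but would not alter the sums.

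**What to change.** In Section 5, replace 500 with the sizes that the plan supports:
- 0.4 mg phase: 383 at April 4, 2017, updated to the final count at April 30, 2017;
- 2 mg phase: goal 100, or 72-120 a year at the stated 6-10 a month (12×6 to 12×10), labelled as a projection;
- projected total: 483 at goal, adjusted once the final 0.4 mg count is entered.

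Then state whether the mortality claim uses the pooled total or one phase, and against what comparator. Recompute the 80% power statement at that size, or withdraw it.

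The cost is protocol wording and one recalculation. The stated size and the power claim become less favourable. No added enrolment, visit or procedure is proposed.

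### Section 5's 80% power for a mortality difference is not delivered on the readings tried, and objective 1 and endpoint 1 state an effect where the data give a count of reported reversals

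*Combined protocol and SAP*

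**What the plan says.** - Section 1, objective 1: "To decrease the number of fatal and nonfatal overdose deaths by use of the naloxone auto-injector". The same section introduces the work as a pilot.
- Section 7, endpoint 1: "Number of fatal over dose deaths and near fatal overdoses averted by use of naloxone auto-injector co-prescribing".
- Section 5, power analysis: "the occurrence of opioid overdose death at the UNM ASAP is approximately 10% annually", followed by "With a sample size of 500 people we will have 80% power to detect a 20% difference in mortality at alpha level of 0.05". It does not give the groups compared, the test, the sidedness, whether 20% is relative or absolute, or the source of the 10%.
- Section 12: kits go to all study subjects. Overdose details, including the clinical outcome, are taken by patient interview and checked in PowerChart only where UNM Hospital was used. Section 16 labels the outcome parameters as self-report.
- Section 3.1: "The previous study at ASAP is a prospective observational study using the naloxone 0.4 mg auto-injector". Section 2 also calls the year-1 work nonrandomized.
- Section 2, year 1: "Only one of the reported overdose reversals was from the study patients at ASAP, while the other 81 overdose reversals were from community members".
- Section 7, endpoint 4, gives the only product contrast: "prospectively analyze the difference in doses (2 mg vs. 0.4 mg) needed to reverse an overdose". Endpoint 2 compares subjects who performed reversals with those who did not.
- Section 13 plans descriptive statistics and two-group tests without naming the groups. Death is not among the variables it lists for testing.

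**The concern.** Events averted and a decrease in deaths are both effects. Each needs a contrast with what would have happened without the kits: a control group, a reference period, or a stated probability of death without naloxone. None is named in Sections 3, 5, 7 or 13. In both named contrasts (2 mg against 0.4 mg, and reversers against non-reversers), kit holders are on both sides.

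The power statement concerns mortality among patients at the clinic, whereas almost all recorded reversals were in other people. A reader of Section 5 would believe that the study is well powered for a mortality difference. A reader of Section 7 could take a count of reversals for a count of deaths prevented. Objectives 2 to 4 are not affected.

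**Working it through.** **Inputs.** From Section 5: p0 = 0.10, N = 500, alpha = 0.05, stated power 80%, a 20% difference. From Section 2: 358 enrolled, 82 reversals, 1 in a study patient and 81 in community members. Sidedness and the scale of the 20% are not stated, so I show the alternatives.

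**Step 1. Try to reproduce the 80%, taking 20% as relative (p1 = 0.08).**

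Two groups of n, pooled variance: power = Φ[(|p0 − p1| − z·SE0)/SE1], where SE0 = sqrt(2·0.09·0.91/n) and SE1 = sqrt((0.09 + 0.0736)/n). For n = 250, two-sided: (0.02 − 1.96·0.02560)/0.02558 = −1.179, so power = 0.119.

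One group of n against a fixed 10%: the same form, with SE0 = sqrt(0.09/n) and SE1 = sqrt(0.0736/n). For n = 500, two-sided: (0.02 − 1.96·0.01342)/0.01213 = −0.519, so power = 0.302 (exact binomial 0.287).

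| Reading of 500 people, 10% to 8% | Two-sided | One-sided |
|---|---|---|
| 250 per group | 12% | 19% |
| 500 per group | 20% | 29% |
| 500 against a fixed 10% | 30% | 43% |

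A relative rise to 12% does no better: 11% two-sided (18% one-sided) with 250 per group, and 33% (44%) against a fixed 10%.

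**Step 2. Take 20% as absolute.** A 20-point fall from 10% is impossible. A 20-point rise to 30%, with 250 per group, gives (0.20 − 1.96·0.03578)/0.03464 = 3.75, which is power over 99.9%. That is not 80%, and it is the opposite of a decrease.

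**Step 3. Try a survival form.** With a hazard ratio of 0.8, one-sided, Schoenfeld's formula gives 4·(1.645 + 0.842)²/(ln 0.8)² = 497 deaths, and Freedman's gives 501. This is close to 500, but as deaths. Section 5 says people: 250 at 10% plus 250 at 8% give 25 + 20 = 45 deaths, for which one-sided power is about 18.5%.

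**Step 4. What 80% would take (two-sided, 10% to 8%).**
- Fixed 10%: [(1.96·0.3 + 0.842·0.2713)/0.02]² = 1,666 subjects.
- Two groups: [(1.96·0.4047 + 0.842·0.4045)/0.02]² = 3,213 per group.
- With 500 people in total, the rate would have to fall to about 6.4% (fixed reference) or 3.7% (250 per group).

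**Step 5. Who is reversed.** 81/82 = 98.8% of year-1 reversals were in community members. Per 100 enrolled this is 81/358 = 22.6 in community members and 1/358 = 0.3 in subjects. Enrolment was rolling, so these are not annual rates. A mortality rate among enrolled subjects would barely reflect these events.

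**The case against.** The best case for the plan has four parts.

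1. *It is a pilot, and the protocol already reports a count.* Sections 1, 2 and 7 give year-1 results as reported or documented reversals, and the word for saving people is put in quotation marks. Endpoint 1 can be read as that count, loosely worded. This stands, and it makes the endpoint fault one of wording. It does not help the power statement, since a pilot that reports a count needs no mortality power.

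2. *The 10% may be meant as a historical reference.* It could be, but Section 5 does not say so and gives no source, and Section 13 contains no such test. Even on that reading, power for a 20% relative change is 30% to 33% two-sided and at most about 44% one-sided.

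3. *500 nearly matches a standard calculation.* It does, as deaths under a one-sided hazard ratio of 0.8. That may be where the number came from, but the text says people.

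4. *A comparison could be described elsewhere.* Part of the protocol between Section 9 and the visible text of Section 12 was not available to me, and Section 13 refers back to Section 12. A comparator stated only there cannot be excluded. Sections 3, 5, 7 and 13, where one would expect it, name none.

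**Conclusion.** The 80% figure is wrong as written. Two-sided power for the relative reduction it appears to describe is about 12% to 30%, depending on the comparison assumed. This takes the stated 10%, 500 people and alpha 0.05 at face value, with complete ascertainment of deaths. The power statement must be fixed.

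The effect wording in objective 1 and endpoint 1 goes beyond what an all-treated cohort with self-reported reversals can show. It should be fixed.

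A reader might infer three stronger things, which the documents do not support:
- That no reading whatever could give 80%. I can say only that none of those tried does, and that 500 does fit as a number of deaths.
- That mortality is tested nowhere in the plan. The available text names no such test, but some text was not available.
- That the investigators will report reversals as deaths averted. Their own year-1 figures are given as reversals, so this is a risk created by the wording and not an established practice.

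**What to change.** (a) Withdraw the mortality power statement from Section 5. If it is kept, state the comparison, the source of the 10%, whether the difference is relative or absolute, the sidedness and the true power (about 12% to 30% two-sided for 10% to 8%), and add the matching test to Section 13.

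(b) Restate endpoint 1 as the number of reported overdose reversals and the rate per 100 enrolled, with follow-up time and reported outcome, shown separately for study subjects and community members. Restate objective 1 as estimating these quantities. Do not describe reversals as deaths averted.

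Both are wording changes, apart from the added test if the power claim is kept. No visit or data item is added. The cost is a more modest headline claim and the loss of a power claim that the study does not have.
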